#### 4. Study Procedures

- a. This is a prospective, randomized, controlled, longitudinal clinical trial that will make use of the following protocol:
  - Patients are admitted to the hospital for acute stroke and undergo work-up including MRI; they are entered into our Clinical Outcomes Database (routine clinical care, database is HIPAA compliant and has prior IRB approval). At this point, or at their first follow-up clinic visit, they will be identified and approached about participation in the study.
  - All patients are scheduled for an appointment in the Bayview Stroke Intervention Clinic (BaSIC) approximately 4-6 weeks +/- 4 weeks post-stroke
  - Seen at 4-6 weeks (routine care)- consented and tested if enrolled (per research protocol, as part of a prior approved study on Stroke Recovery)
  - Those meeting inclusion criteria for the Mindfulness and MEG study will be consented, randomized, and undergo the following additional procedures:
    - 1 month MEG visit at the University of Maryland (UMD, our current partner for our ongoing MEG study)- brain activity will be measured at rest and during cognitive tasks
    - EITHER 8 weeks of either MBSR Training and guided meditation using provided resources or participation in our bi-monthly Stroke Support Group
    - Repeat MEG following intervention (approximately 4-6 months post-stroke)
      - UMD MEG Protocol:
        - Magnetic fields will be recorded using a 275-channel whole-head MEG system (KIT System)

The MEG System non- invasively measures the magnetoencephalographic (MEG) signals produced by electrically active tissue of the brain. These signals are recorded by a computerized data acquisition system, displayed, and may then be interpreted by trained physicians to help localize these active areas. The location may then be correlated with anatomical information of the brain. MEG is routinely used to identify the locations of visual, auditory, somatosensory, and motor cortex in the brain. \* MEG is also used to non-invasively locate regions of epileptic activity within the brain. The localization information provided by MEG may be used, in conjunction with other diagnostic data, in neurosurgical planning.

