**To determine the effect of MBSR on abnormal cerebral activation patterns on MEG after stroke:**

- Participants will undergo neuroimaging at 1 and 6 months post-stroke. Participants in the MBSR and SSG will be compared to a previously collected group of controls with no infarct. Source localized whole brain activation will be assessed to determine overall differences in space and time between each group (MBSR v SSG) versus controls for each time point. Cluster-based permutation tests (based on independent measures t values) will then be performed to evaluate mean differences in activation for ROIs between groups at each time point. Paired t values will allow for evaluation of changes over time within each group. Amplitude of peak activation and spike latency will be assessed. ANCOVA will allow for adjustment of potential confounders.
- *Sample Size.* We have been able to demonstrate results at or approaching statistical significance for our current cohort of patients with minor stroke versus controls after enrolling only 9 participants. This number is similar to many other published studies evaluating differences in activation patterns on MEG. We do anticipate less of a difference when comparing stroke patients to other stroke patients, and will therefore increase our sample size to at least 20 individuals in each group. There remains a chance given the potential for improvement in both groups, that we may still be inadequately powered to detect long-term outcomes in this pilot study; however results will also allow treatment effect estimates that will inform a larger clinical trial.

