**To determine the impact of mindfulness on post-stroke cognitive impairment:**

- The MoCA and cognitive battery will be administered at 1 and 6 months post-stroke. T-tests and chi square analysis will compare cognitive performance (MoCA, global cognitive score, and individual cognitive tests) pre- and post-intervention for each group (MoCA cutoff <26), and MBSR v SSG participants at each time point.

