**To determine the impact of mindfulness on post-stroke depression:**

- Participants will be administered the PHQ-9 pre- and post-intervention. Paired t-tests will be used to evaluate for significant differences in scores between time points using each score as a continuous variable. Chi square analysis will be used to evaluate presence or absence of moderate depression (PHQ9 score >9). Independent t-tests and chi square analysis will compare scores of MBSR versus SSG participants for each time point.
- *Sample Size.* Based on prior MBSR studies, we anticipate that this will show a greater clinical effect than change in MoCA, giving us more than adequate power to detect differences with this sample size.

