### **Changes to the Protocol to Continue Research Without In-Person Visits (in the setting of worsening pandemic)**

**Consent-** We will expand consent to include remote consent facilitated by video conferencing if needed during their video televisit follow-up. The consent will be reviewed with the patient as previously described either by phone or video. Verbal consent will be obtained. They will be provided with a copy of the consent form via email/fax/mail and will send back in their signed copy (following verbal consent).

**Clinic Visits/Testing-** We have adapted the cognitive tasks and testing batteries so that they can be performed remotely via video conferencing and we can see them remotely via telehealth visits for their clinical/research follow-up visits (participants will need a laptop with a camera for remote/telehealth visits).

When remote assessment/therapy is not feasible, we will conduct in-person visits. In that case, prior to each scheduled visit, we will call participants and screen for COVID-19 symptoms and exposure. If a participant reports symptoms or exposure, the in-person visit will be cancelled. In-person visits will be rescheduled pending medical evaluation of signs/symptoms or after 14-day self-quarantine if there was exposure or potential exposure. The research team will reference JHU policies for self-screening and will defer any in-person or on-campus activities if they report COVID-19 symptoms and another member of the team will conduct the visit if possible. During each visit, participants and the research team will wear masks. If they do not provide their own mask, we will provide a disposable mask for them and practice social distancing whenever possible along with proper hand hygiene practices. All assessment/therapy materials and work surfaces (tables, doorknobs) will be disinfected after each session.

**Interventions-** Currently, both the weekly Stroke Support Group and Mindfulness Based Stress Reduction group are in person. If it is safe for in-person encounters, for the added potential benefit of socialization, we will continue to hold them in small groups. We will take all of the necessary safety precautions described above.

In addition, have adapted both interventions so that they can be available over telecommunication platforms (eg. Zoom) depending on the severity of the pandemic over the study period.

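### Both arms are treated in small groups, but the post-intervention MBSR v SSG analyses make no allowance for correlation within a group, so standard errors may be too small

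*Combined protocol and SAP*

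**What the plan says.** **Delivery.** Section 4 (Study Procedures) assigns participants to "8 weeks of either MBSR Training and guided meditation using provided resources or participation in our bi-monthly Stroke Support Group". The Interventions paragraph of the pandemic changes says that "both the weekly Stroke Support Group and Mindfulness Based Stress Reduction group are in person", and continues: "If it is safe for in-person encounters, for the added potential benefit of socialization, we will continue to hold them in small groups". Both interventions have also been adapted for video platforms. Group size, number of groups, instructor arrangements, and whether membership is closed or rolling are not stated.

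**Analysis.** All of the following is in Section 7.
- Depression: "Independent t-tests and chi square analysis will compare scores of MBSR versus SSG participants for each time point".
- Cognition: "T-tests and chi square analysis will compare cognitive performance", including "MBSR v SSG participants at each time point".
- MEG: permutation tests built on independent-samples t values, with ANCOVA for confounders. The word cluster there appears to refer to clusters in the MEG signal, not to treatment groups.
- Satisfaction and recovery: regression models.
- Section 7c: linear regression if confounders are unevenly distributed. The listed examples are participation, age, sex, education, antidepressant use and comorbidity; group and instructor are not among them.

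No random effect, cluster-robust standard error or design effect appears anywhere.

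**Size.** The only design figure is to "increase our sample size to at least 20 individuals in each group". It comes without an effect size, SD, significance level or numeric power.

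**The concern.** Patients are randomised as individuals but then treated together. Members of one class share an instructor, peers, a calendar period and possibly a delivery mode (in person or video). Any of these can make their later scores resemble one another.

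The protocol itself treats group contact as potentially active. It keeps sessions in person "for the added potential benefit of socialization, we will continue to hold them in small groups", and Section 4e uses the support group to adjust for socialization. Self-reported outcomes such as the PHQ-9 and satisfaction are plausible places for such an influence to show.

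If the correlation is positive, a test that assumes independence overstates the information in the data, and one unusually good or poor class can be read as an effect of MBSR. Section 7 also says that the treatment-effect estimates will inform a larger trial. Understated standard errors would carry into that planning. Without a recorded group identifier, the ICC that a larger group-delivered trial needs could not be estimated even roughly.

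**Working it through.** **The plan's own figure.** The 20 per group cannot be reproduced, because the effect size, SD, significance level and power are missing. For orientation, at an assumed two-sided 5%, 20 v 20 gives 80% power for a standardised difference of about 0.91 (t-test) and 35% power for 0.5 (normal approximation).

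**Inputs.**
- From the documents: 20 per arm, group delivery in both arms, independent-samples tests.
- Assumed: two-sided 5%; equal closed groups of m = 5 or 10 (four or two groups per arm), or one group of 20 per arm; ICC 0.01, 0.05 or 0.10.

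**Formulas.** Design effect DEFF = 1 + (m − 1) × ICC. True SE / naive SE = √DEFF. Approximate actual type I error = 2 × [1 − Φ(1.96/√DEFF)]. This was checked by simulating the ordinary two-sample t-test under the null, 50,000 runs per cell.

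Example, m = 10 and ICC 0.05: DEFF = 1 + 9 × 0.05 = 1.45; √1.45 = 1.204; 1.96/1.204 = 1.628; approximate type I error 10.4%, simulated 10.5%.

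| m | ICC | DEFF | SE ratio | Formula | Simulated, both arms clustered | Simulated, one arm clustered |
|---|---|---|---|---|---|---|
| 5 | 0.01 | 1.04 | 1.02 | 5.5% | 5.3% | 5.3% |
| 5 | 0.05 | 1.20 | 1.10 | 7.4% | 7.4% | 6.0% |
| 5 | 0.10 | 1.40 | 1.18 | 9.8% | 9.9% | 7.6% |
| 10 | 0.01 | 1.09 | 1.04 | 6.0% | 6.0% | 5.7% |
| 10 | 0.05 | 1.45 | 1.20 | 10.4% | 10.5% | 7.7% |
| 10 | 0.10 | 1.90 | 1.38 | 15.5% | 15.9% | 10.6% |
| 20 | 0.01 | 1.19 | 1.09 | 7.2% | 7.3% | 6.0% |
| 20 | 0.05 | 1.95 | 1.40 | 16.0% | 16.7% | 10.9% |
| 20 | 0.10 | 2.90 | 1.70 | 25.0% | 26.6% | 16.6% |

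A repeat run with both arms clustered gave 5.4% to 9.9% for groups of 5 and 6.1% to 16.1% for groups of 10. Differences of 0.1 to 0.2 points are simulation error. At ICC 0 the test holds its level, about 5%.

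**Effective size.** At ICC 0.05, 20 per arm carries the information of 20/1.20 = 16.7 independent patients (groups of 5) or 20/1.45 = 13.8 (groups of 10).

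**Price of replacing the planned test.** Take a t-test on group means, d = 0.9 and a true ICC of zero. The noncentrality is 0.9/√(2/20) = 2.85 in every case; only the degrees of freedom change.
- Ordinary t-test, 38 df: power 79%.
- Four groups per arm, 6 df: power 66%.
- Two groups per arm, 2 df (critical t 4.30): power 36%.

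**The case against.** **Inflation is conditional.** A reader might infer that the standard errors are too small and that the false-positive rate does exceed 5%. The documents do not support that. Both need a positive ICC, and neither the ICC nor the group size is given; even the 5% level is an assumption. At ICC 0.01 with groups of 5 the excess is negligible. This stands, and the point is worded accordingly.

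**Not every between-arm test is exposed.** The plan compares arms at each time point, including before any group has met. Group delivery cannot disturb those comparisons. This stands too. The unit permuted in the MEG tests is also not stated.

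**The group structure is unknown.** The support group reads as an existing service run by the stroke centre (Section 11), and may be one continuing group with rolling attendance. In that case group and arm are confounded and no model can separate them. The MBSR arm also includes guided meditation, whose share is not stated, and either arm may move to video. If only one arm clusters, the inflation is smaller.

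**Replacing the tests would cost a great deal of power.** The drop from 79% to 66% or 36% is real, and it occurs even when there is no clustering. It is a sound argument against making a cluster-level test the main analysis.

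**This is a pilot.** Section 7 admits possible inadequate power, and with equal-sized groups and random group effects the expected treatment estimate is not biased. That lowers the stakes. It does not excuse leaving group membership out of the analysis, since precision is what a planner of the larger trial would rely on, and Section 7 also claims more than adequate power for the PHQ-9.

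**Conclusion.** The omission is certain: both arms are delivered in groups, and no post-intervention between-arm analysis allows for it. Its consequence depends on quantities that the documents do not give.

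Assuming a two-sided 5% test, 20 per arm, equal closed groups and clustering in both arms, the type I error runs over ICC 0.01 to 0.10 from about 5.4% to 9.9% for groups of 5 and from about 6.1% to 16.1% for groups of 10. The true standard error is then 1.02 to 1.38 times the naive one. With a single group of 20 per arm, the error is about 17% at ICC 0.05.

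The top of these ranges should not be read as the trial's actual error rate; it is one corner of an assumed grid. This is a modest, conditional weakness with a cheap remedy, and not grounds for discarding the planned tests.

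**What to change.** 1. **Describe the groups.** State the planned number and size of groups in each arm, whether membership is closed or rolling, and who leads them. The support group is called weekly in the pandemic changes but bi-monthly in the Abstract and Sections 4 and 11; these passages must be reconciled.
2. **Record** the group and instructor for every participant.
3. **Keep the planned tests.** Beside each post-intervention MBSR v SSG result, including MEG region-of-interest means, report a sensitivity analysis. Where there are enough groups, use a random group effect (or a partially nested model if only one arm is grouped) with Kenward-Roger or Satterthwaite degrees of freedom. Otherwise, multiply the naive standard error by √[1 + (m − 1) × ICC] at ICC 0.05 and 0.10. With both arms clustered, that is 1.10 and 1.18 for groups of 5, or 1.20 and 1.38 for groups of 10.
4. **Report the ICC** for planning the larger trial, with a statement that it is imprecise.
5. **If one continuing group serves an arm,** state that the group effect cannot be separated from the arm effect, and limit the conclusion accordingly.

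Cost: one or two data fields and a few sentences of SAP text, with no extra patients or visits. The downside is wider intervals and less favourable p-values in the sensitivity analysis.

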## 7. Study Statistics

- a. Primary outcome variables include: MEG- changes in spectral properties and an estimate of the localization of spontaneous brain activity during resting state, functional connectivity during resting state. Clinical- performance on the MOCA and other cognitive measures (as part of the Recovery Study), patient-reported outcomes: fatigue, depression, satisfaction, quality of life.
- b. Secondary outcome variables include: changes in spectral properties, spontaneous brain activity, and functional connectivity during completion of various cognitive tasks.
- c. We will use an intention-to-treat analysis; however, we will adjust for degree of participation and consider an additional exploratory per-protocol analysis. For those lost-to-follow-up, data will be censored at the time they are lost. In addition to the proposed analyses, if there is evidence for an uneven distribution of confounding factors across treatment and control groups, we will perform multivariable linear regression to adjust for confounders (eg. degree of participation, age, sex, level of education, antidepressant use, and major medical co-morbidities (Charlson Comorbidity Index)).

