## 9. Benefits

- a. Participants taking part in either MBSR or SSG may derive benefit from the intervention. In addition, they will be advancing the field so that future patients with minor stroke will recover faster and more fully.

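### The PHQ-9 claim of more than adequate power has no effect size behind it; at 20 per arm the between-arm t-test reaches 80% power only for a difference of about 0.91 SD

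*Combined protocol and SAP*

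**What the plan says.** The Sample Size bullet under the depression heading in section 7 claims ample power for PHQ-9: "giving us more than adequate power to detect differences with this sample size". The reason it offers is an expected effect, not a calculation: "Based on prior MBSR studies, we anticipate that this will show a greater clinical effect than change in MoCA". The analysis bullet above it plans paired t-tests for change over time, a chi-square test on PHQ-9 above 9, and, between arms: "Independent t-tests and chi square analysis will compare scores of MBSR versus SSG participants for each time point".

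The sample size it relies on is set in the MEG part of section 7. There the sponsor reports results at or near significance for "patients with minor stroke versus controls after enrolling only 9 participants", expects a smaller contrast between two groups of stroke patients, and so "will therefore increase our sample size to at least 20 individuals in each group". That paragraph also warns that, because both groups may improve, "we may still be inadequately powered to detect long-term outcomes in this pilot study", and says that the effect estimates will inform a larger trial.

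Section 7a lists depression among the primary outcomes, and it is Objective 3 in section 2. Section 7c says of dropouts: "For those lost-to-follow-up, data will be censored at the time they are lost". It gives no expected rate of loss.

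**The concern.** A power statement needs an effect, a measure of spread, an alpha and a target. This one has none. It rests on earlier MBSR studies cited without figures and on a comparison with MoCA, and the cognitive part of section 7 gives neither a MoCA effect nor a MoCA sample-size calculation. The figure of 20 per group did not come from PHQ-9 at all.

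The comparator makes a large contrast harder to take for granted. MBSR is compared with a support group, and section 9 says: "Participants taking part in either MBSR or SSG may derive benefit from the intervention". The question is how much better MBSR does than another activity that may itself help, not how far PHQ-9 falls after MBSR.

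What is at stake is how a null result is read. If readers are told that power was more than adequate, a non-significant PHQ-9 comparison looks like evidence against an effect and could lead the larger trial to drop the outcome. At realistic sample sizes for this pilot, such a result would say little.

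**Working it through.** **The plan's own figure.** There is none to reproduce, because power is given only in words. The calculation therefore works in SD units and asks what difference the planned test can detect.

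**Inputs**
- n = 20 per arm: the stated minimum (section 7, MEG, Sample Size). Equal allocation is inferred from the equal minimum group sizes.
- Test: independent t-test between arms (section 7, depression).
- Two-sided alpha 0.05 and 80% power: assumed, since the plan states neither.
- Effect size and SD: not given, so a range is shown. All effect values below are illustrative.

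**Method.** With a standardised difference d, the test statistic follows a noncentral t distribution with 2n − 2 = 38 degrees of freedom and noncentrality d × √(n/2) = d × √10. The critical value is 2.024.

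| True difference | Noncentrality | Power, 20 per arm |
|---|---|---|
| 0.5 SD | 1.58 | 34% |
| 0.8 SD | 2.53 | 69% |
| 0.9 SD | 2.85 | 79% |
| 1.0 SD | 3.16 | 87% |

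Solving for d gives 0.909 SD for 80% power and 1.052 SD for 90%. As a check, the normal approximation (1.960 + 0.842) × √(2/20) gives 0.886 SD.

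**Precision.** The unadjusted 95% interval half-width is 2.024 × √(2/20) = 0.640 SD.

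**Sensitivity of the 80% figure**

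| Change in assumption | Detectable difference |
|---|---|
| 15% lost, 17 analysed per arm (assumed) | 0.99 SD |
| 25 per arm | 0.81 SD |
| 30 per arm | 0.74 SD |
| 20 per arm, one-sided 0.05 | 0.80 SD |

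In the other direction, 80% power at two-sided 0.05 takes 64 per arm for 0.5 SD and 26 per arm for 0.8 SD.

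**Other tests planned for PHQ-9**
- Paired t-test within one arm, n = 20: 80% power at 0.66 SD of the change score. This does not compare the arms.
- Chi-square on PHQ-9 above 9, 20 per arm, assuming 40% above the cut-off in the support group: 28% power if MBSR halves this to 20%. Reaching 80% power needs a fall to about 4%.

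**Baseline adjustment, if it were adopted.** ANCOVA on baseline PHQ-9 multiplies the SD by √(1 − r²) and uses 37 degrees of freedom. With r = 0.6 (assumed), the factor is 0.8, the detectable difference is 0.73 SD and the half-width is 2.026 × 0.8 × √(2/20) = 0.51 SD. The detectable difference runs from 0.83 SD at r = 0.4 to 0.65 SD at r = 0.7. The depression analysis plans unadjusted t-tests. Section 7c brings in regression only if confounders are unevenly distributed, and baseline PHQ-9 is not among its examples.

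**The case against.** **The study is a pilot and already admits limited power.** The MEG paragraph does so, and its reason, improvement in both groups, is the same between-arm problem raised here. It also presents the results as estimates for a later trial. This stands in part: a careful reader of all of section 7 would be forewarned. But the caveat sits under the MEG heading and concerns long-term outcomes. The depression paragraph then says the opposite about PHQ-9, and the reason given for the caveat applies to PHQ-9 as well.

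**The claim may be true.** The earlier studies it relies on could show large effects, and they cannot be seen from these documents. This stands. The finding is that the claim lacks support. The 0.5 SD used for illustration is not in the plan; at 0.8 SD the miss rate is 31%, and at 1.0 SD it is 13%.

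**The sentence may refer to the paired tests.** It names no test, and its comparator is a change in MoCA. That reading is possible and lowers the requirement to 0.66 SD of change. It does not rescue the claim for the trial's hypothesis, which the abstract (section 1) frames as MBSR against the support group. A within-arm change mixes any treatment effect with natural recovery.

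**The sponsor should first be asked for the effect size.** This is fair, and the fix leaves room for it.

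**Conclusion.** The concern holds. The PHQ-9 power claim has no quantitative basis in the documents, and the design supports it only for very large differences: about 0.91 SD for 80% power and 1.05 SD for 90%, with 20 per arm and two-sided alpha 0.05. A true difference of 0.5 SD would be missed about two times in three (1 − 0.34 = 0.66).

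The figures rest on assumed alpha and power, on equal arms and on 20 analysed per arm. Because 20 is a minimum, more recruits would lower the detectable difference, while dropout would raise it. Even with 30 per arm it is 0.74 SD, so the conclusion does not turn on these choices. The correction should be made because depression is a listed primary outcome and the results are meant to shape a larger trial.

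**What to change.** In the depression Sample Size bullet of section 7, delete the claim of more than adequate power and put in its place:

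> With 20 per arm and two-sided alpha 0.05, the independent t-test on follow-up PHQ-9 has 80% power for a difference of about 0.91 SD; the unadjusted 95% confidence interval half-width is about 0.64 SD. The PHQ-9 difference will be reported as a pilot estimate with its confidence interval, and a non-significant result will not be read as no effect.

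If the sponsor has a between-arm PHQ-9 effect from the earlier studies, it should be added beside this text with its SD and source, so that readers can judge whether 0.91 SD is plausible. The baseline-adjusted figures (about 0.73 SD detectable and 0.51 SD half-width, assuming r = 0.6) should be quoted only if the plan first makes ANCOVA on baseline PHQ-9 the between-arm analysis.

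The cost is one paragraph of wording and a less favourable power statement. Enrolment, visits and planned tests stay as they are, and no increase in sample size is proposed.
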